#### **4.8.3    Rescue Medications, Treatments, and Procedures**

Rescue medication, as determined by the Investigator, is permitted for a maximum of 7 consecutive days, provided it is consistent with the prohibitions and restrictions in [Appendix A](#) and [Appendix B](#).

### **5    INVESTIGATIONAL PRODUCT**

#### **5.1    Investigational Product Description**

The investigational product will be pimavanserin 10 mg (provided as 1×10 mg capsule), pimavanserin 20 mg (provided as 1×20 mg capsule), or pimavanserin 34 mg (provided as 1×34 mg capsule). Capsules will be administered orally as a single dose once daily.

*Pimavanserin dosages below:*

Pimavanserin 10 mg (provided as 1×10 mg capsule)

Pimavanserin 20 mg (provided as 1×20 mg capsule)

Pimavanserin 34 mg (provided as 1×34 mg capsule)

#### **5.1.1    Formulation, Appearance, Packaging, and Labeling**

The Sponsor will supply pimavanserin 10 mg, 20 mg and 34 mg capsules.

Pimavanserin 10 mg, 20 mg, and 34 mg capsules, are white to off-white capsules.

Each 34 mg pimavanserin capsule contains 40 mg of pimavanserin tartrate, which is equivalent to 34 mg of pimavanserin free base.

Each 20 mg pimavanserin capsule contains 23.5 mg of pimavanserin tartrate, which is equivalent to 20 mg of pimavanserin free base.

Each 10 mg pimavanserin capsule contains 11.8 mg of pimavanserin tartrate, which is equivalent to 10 mg of pimavanserin free base.

Inactive ingredients include magnesium stearate, microcrystalline cellulose, and the components of the capsule shell (hypromellose and titanium dioxide).

Pimavanserin capsules are manufactured under current Good Manufacturing Practice.

Pimavanserin capsules will be provided in kits containing two blister cards, with each card containing 10 capsules in a blister strip (total 20 capsules per kit). Each kit will be labeled as required per country requirement.

During the treatment period, study drug will be distributed in a quantity sufficient to ensure the subject has an adequate supply of study drug between study visits.

### **5.1.2 Product Storage and Stability**

Investigational product must be stored in a secure area with restricted access, not above 25°C (77°F), and according to local and national regulations. To prevent potential capsule color fading, protect from light.

### **5.1.3 Dosing and Administration**

At the Baseline visit of Study ACP-103-070, study drug will be dispensed to the subject to take home. The subject and their parent/LAR will be provided instructions for the subject's first dose of study drug on the day after the Baseline visit.

Each daily dose consists of one capsule. Subjects should be instructed to take one capsule, orally, once daily, in the morning, at the same time every day. Subjects should be instructed to not to open the capsules. The capsules may be taken with or without food.

#### **5.1.3.1 Dose Modification**

All subjects will receive the "low dose" for their age group for the first two weeks of the study. After the Week 2 visit the dose may be increased to the "high dose" based on the Investigator's assessment of clinical response. After the Week 2 visit, and up to and including the Week 20 visit, dose adjustments, either increases or decreases, may be made at any clinic visit (scheduled or unscheduled), based on the Investigator's assessment of clinical response and tolerability.

No further dose adjustments are allowed after the Week 20 visit.

#### **5.1.4 Blinding**

This is an open-label study.

#### **5.1.5 Study Drug Compliance**

The Investigator or designated study center personnel will maintain a log of all study drug dispensed and returned during the study. Study drug supplies for each subject will be inventoried

and accounted for throughout the study to verify the subject's compliance with the dosage regimen. Subjects will be counseled regarding compliance at every visit. Subjects who have <80% or >120% compliance may be discontinued from the study. If a subject shows significant undercompliance (<80%) between any two scheduled visits, the Medical Monitor should be notified to determine if the subject remains eligible for the study and whether the incident should be considered a protocol deviation.

If a subject misses one dose of study drug, he or she should not take an extra dose the next day.

### **5.1.6 Overdose**

An overdose is a deliberate or inadvertent administration of a treatment at a dose higher than the maximum recommended dose per protocol. It must be reported using the Sponsor's Overdose Reporting form, irrespective of outcome, even if toxic effects were not observed ([Section 7.4.4](#)). All events of overdose are to be captured as protocol deviations.

## **5.2 Investigational Product Accountability Procedures**

The Investigator or designee will keep current and accurate records of the study drug product dispensed, used, and returned for each subject to assure the regulatory authority and the Sponsor that the study drug is being handled appropriately. Subjects should be instructed to return all packaging and unused study drug to the Investigator at regularly scheduled clinic visits and ET visits. Any study drug supplied is for use in this study only and should not be used for any other purpose.

At appropriate intervals during the study, study drug reconciliation will be performed by the Sponsor (or designee) who may return appropriate unused study drug and used and unused packaging to the Sponsor's designee for destruction.

At the conclusion of the study, final study drug reconciliation will be conducted at the site. Final study drug accountability documentation will be maintained at both the site and at the Sponsor. Any remaining unused study drug and all used and unused packaging will be sent back to the Sponsor's designee for destruction, as allowed by country specific regulations. Documentation of study drug destruction will be recorded and maintained by both the Sponsor and the Sponsor's designee.

## **6 STUDY ASSESSMENTS**

Study specific assessments are detailed below. All assessments will be completed according to the schedule described in [Table S-1](#). Every effort should be made to complete the required procedures and evaluations at the designated visits and times.

For scales that require caregiver input, the caregiver should be the parent/LAR or designee. A designee should be a family member, adult and responsible, living with or in very frequent

contact with the subject participating in the study, who is committed to providing responses for the caregiver-reported scales for the duration of Studies ACP-103-069 and ACP-103-070.

Caregivers providing input for the ABC, RBS-R, and CGSQ scales will be trained in accurate symptom reporting (ASR) prior to completing the scales. ASR training should be done at Screening in the antecedent study (Study ACP-103-069) before the caregiver completes any scales, and repeated whenever there is a change in caregiver or if the site feels a caregiver requires retraining.

## **6.1 Baseline Assessments**

Subject consent for the present study must be obtained prior to the final procedures being performed at the EOT visit of the antecedent double-blind study and before any new procedures are performed for Study ACP-103-070. Data from the EOT procedures of antecedent double-blind study will be carried over to the ACP-103-070 study to be included as baseline information for the present study and this visit will be considered Baseline (Visit 1). Subject eligibility will be assessed by the site and the Sponsor through an eligibility review process.

### **6.1.1 Physical Examination and Self- or Caregiver-reported Tanner Staging**

See [Section 6.4.1](#)

### **6.1.2 Vital Signs**

See [Section 6.4.2](#).

### **6.1.3 Height, Weight, and Body Mass Index**

See [Section 6.4.1](#).

### **6.1.4 12-lead ECG**

See [Section 6.4.3](#).

### **6.1.5 Clinical Laboratory Tests**

See [Section 6.4.4](#).

### **6.1.6 Pregnancy Test**

See [Section 6.4.4](#).

### **6.1.7 Urine Toxicology (Drug) Screen**

See [Section 6.4.4](#).

### **6.1.8 Aberrant Behavior Checklist**

See [Section 6.2.1](#).

### **6.1.9 CGI-S**

See [Section 6.2.2.](#)

### **6.1.10 CGI-I**

See [Section 6.2.3](#)

### **6.1.11 RBS-R**

See [Section 6.2.4.](#)

### **6.1.12 VABS-Socialization**

See [Section 6.2.5.](#)

### **6.1.13 CGSQ**

See [Section 6.2.6.](#)

### **6.1.14 C-SSRS**

See [Section 6.3.1](#)

### **6.1.15 ESRS-A**

See [Section 6.3.2](#)

### **6.1.16 Concomitant Medications and Adverse Events**

All medications used from Baseline until completion of the safety follow up visit are to be recorded ([Section 4.8](#)).

All adverse events ([Section 7](#)) from Baseline until completion of the safety follow up visit are to be recorded.

## **6.2 Efficacy Assessments**

### **6.2.1 Aberrant Behavior Checklist**

The Aberrant Behavior Checklist (ABC) is a caregiver-rated scale comprised of five empirically-derived subscales encompassing 58 items that describe various behavior problems ([Aman et al. 1985; Kaat et al. 2014](#)). The subscales have been labeled:

- I. Irritability (irritability, agitation, and crying) (15 items)
- II. Lethargy (lethargy and social withdrawal) (16 items)
- III. Stereotypic Behavior (7 items)
- IV. Hyperactivity (hyperactivity and noncompliance) (16 items)
- V. Inappropriate Speech (4 items)

The ABC will be administered at Baseline, and at all visits from Week 2 through Week 52. A score for each item ranges from 0 indicating “not at all a problem” to 3 indicating “the problem is severe in degree”. Subscale scores are calculated by summing the items within that subscale. Higher scores indicate greater impairment.

The reliable caregiver identified upon subject’s ACP-103-070 Baseline visit will complete the rating scale. A clinician will be available to assist the caregiver during completion of the questionnaire.

This assessment will take approximately 10 to 20 minutes to complete.

The same rater or clinician should perform the ABC throughout the study together with the same caregiver as established at the Baseline visit.

#### **6.2.2 CGI-S**

The CGI-S is a clinician-rated, 7-point scale that is designed to rate the severity of the subject's illness, in this case irritability associated with ASD, at the time of assessment, making use of the clinician's judgment and past experience with subjects who have the same disorder (Guy 1976). The CGI-S of irritability will be administered at Baseline, and at all visits from Week 2 through Week 52. The same clinician should administer the CGI-S of irritability throughout the study as established at the Baseline visit.

#### **6.2.3 CGI-I**

The CGI-I is a clinician-rated, 7-point scale that is designed to assess how much the subject's illness, in this case irritability associated with ASD, has improved or worsened relative to a baseline state at the beginning of the intervention (Guy 1976). In this study, improvement or worsening is assessed relative to the baseline status in the antecedent double-blind study.

The CGI-I of irritability will be administered at Baseline, and at all visits from Week 2 through Week 52.

The same clinician should administer the CGI-I of irritability throughout the study as established at the Baseline visit.

#### **6.2.4 Repetitive Behavior Scale-Revised**

The Repetitive Behavior Scale-Revised (RBS-R) (Lam and Aman 2007) is a 43-item parent/caregiver-facing questionnaire. Items are conceptually grouped into six subscales:

- stereotyped behavior (movements with no obvious purpose that are repeated in a similar manner)
- self-injurious behavior (actions that cause or have the potential to cause redness, bruising, or other injury to the body)

- compulsive behavior (behavior that is repeated and performed according to a rule or involves things being done “just so”)
- ritualistic behavior (performing activities of daily living in a similar manner)
- sameness behavior (resistance to change, insisting that things stay the same)
- restricted behavior (limited range of focus, interest, or activity)

Items are rated on a 4-point Likert scale ranging from (0) “behavior does not occur” to (3) “behavior occurs and is a severe problem”, and raters are asked to refer to the previous month when completing the scale.

The RBS-R will be administered at Baseline, and at the Week 12, Week 28, Week 36, Week 44, and Week 52 visits. This scale will take approximately 20 to 30 minutes to complete.

The same rater or clinician should perform the RBS-R throughout the study together with the same caregiver as established at the Baseline visit.

#### **6.2.5 Vineland Adaptive Behavior Scales—Socialization**

The Vineland Adaptive Behavior Scales (VABS) is a parent/caregiver-facing measure of adaptive behavior, organized into three domains: communication, daily living skills, and socialization (Sparrow et al. 2016). Only the socialization domain will be used in this study.

The VABS-Socialization will be administered at Baseline, and at the Week 12, Week 28, Week 36, Week 44, and Week 52 visits.

The same rater or clinician should perform the VABS-Socialization together with the same caregiver throughout the study as established at baseline visit.

#### **6.2.6 Caregiver Strain Questionnaire**

The CGSQ (Brannan et al. 1997) is a 21-item parent/caregiver-facing questionnaire of self-reported strain experienced since last visit by parents/caregivers and families of youth with emotional problems. Responses are on a 5-point Likert scale ranging from (1) “not at all a problem” to (5) “very much a problem”.

The following areas of strain are included:

- disruption of family life and relationships
- demands on time
- negative mental and physical health effects for any member
- financial strain
- sacrifice

- disruption of social/community life
- worry and guilt
- fatigue and strain
- embarrassment
- child-caregiver relationship

The CGSQ will be administered at Baseline, and at the Week 6, Week 20, Week 28, Week 36, Week 44, and Week 52 visits.

The same rater or clinician should perform the CGSQ together with the same caregiver throughout the study as established at Baseline visit.

### **6.3 Safety Scales**

#### **6.3.1 Columbia–Suicide Severity Rating Scale**

The C-SSRS monitors changes in suicidal thinking and behavior over time, in order to determine risk ([Posner et al. 2011](#)). The following four constructs are measured: the severity of ideation, the intensity of ideation, behavior, and lethality.

The C-SSRS will be used to assess suicidal ideations and behaviors; the Since Last Visit version will be administered at Baseline, and at all subsequent visits. The C-SSRS results for each subject should be reviewed by the Investigator at each visit. If at any time the C-SSRS results for a given subject reveal potential suicidality, then the Investigator should assess the clinical significance of such results. If a clinically significant risk of suicidality is identified for a subject, then the Investigator should discontinue the subject and implement appropriate treatment ([Sections 4.4 and 3.1.2](#)).

The C-SSRS will be administered at Baseline, at all visits from Week 2 through Week 52, and at unscheduled visits.

The same rater or clinician should perform the C-SSRS together with the same caregiver throughout the study as established at Baseline visit.

#### **6.3.2 Extrapyramidal Symptom Rating Scale–Abbreviated**

The ESRS ([Chouinard and Margolese 2005](#)) was developed to assess drug induced movement disorders such as parkinsonism, akathisia, dystonia and tardive dyskinesia with established reliability, validity, and sensitivity. It consists of a questionnaire of parkinsonian symptoms, physician examination of parkinsonism, dyskinetic movements, and global impression of tardive dyskinesia. The ESRS-A, an accepted modified form of the original ESRS, will be used during

the study to monitor for any worsening in extrapyramidal symptoms or signs at scheduled and unscheduled visits.

The ESRS-A will be administered at Baseline, at all visits from Week 2 through Week 52, and at unscheduled visits.

The same rater or clinician should perform the ESRS-A together with the same caregiver throughout the study as established at Baseline visit.

## 6.4 Safety Assessments

As known potential class side effects of antipsychotics, the following adverse events will be actively monitored, including hyperglycemia, leucopenia/neutropenia/agranulocytosis, orthostatic hypotension/bradycardia/syncope, QTc prolongation, akathisia and other extrapyramidal symptoms, weight gain, and somnolence. Criteria for identifying potentially clinically important laboratory values, ECG values, and vital signs are presented in [Appendix C](#), [Appendix D](#), and [Appendix F](#), respectively; and criteria for identifying additional ECG measurements of potential clinical relevance for Medical Monitoring purposes are presented in [Appendix E](#).

Circumstances may arise (e.g., pandemic, natural disaster, political upheaval, or technical issues) when on-site assessments of safety measures may not be possible. In those cases, assessments may be performed at the subject's place of residence either in person or via video technology or telephone, where possible. If a subject is unable to come to the site for lab draws and the site is unable to travel to the subject's place of residence, the subject may visit a local lab to obtain all safety labs. The Investigator must contact the Medical Monitor for approval with the plan. Sites must keep a log to identify details of all visits that are administered remotely.

### 6.4.1 Physical Examination and Self- or Caregiver-reported Tanner Staging

A general physical examination will be conducted.

Height will be measured and reported.

Weight will be measured and reported.

Body mass index will be calculated using the following formula:

$Weight (kg) / [height (m)]^2$ .

Tanner staging is a scale of physical development in children, adolescents, and adults. The scale defines physical measurements of development based on external primary and secondary sex characteristics, such as the size of the breasts, genitals, testicular volume and development of pubic hair ([Marshall and Tanner 1969](#); [Marshall and Tanner 1970](#)).

A physical examination will be administered, and Tanner staging will be reported (either by the subject or the subject's caregiver), at Baseline, and at the Week 12, Week 28, Week 44, and Week 52 visits.

Height (as measured by a stadiometer), weight, and BMI will be measured at Baseline, at all visits from Week 2 through Week 52, and at unscheduled visits.

#### **6.4.2 Vital Signs**

Vital signs will include body temperature, resting respiration rate, sitting (or supine) systolic and diastolic blood pressure, and pulse rate. The sitting (or supine) blood pressure should be measured after the subject has been sitting (or supine) for  $\geq 3$  minutes. If the initial blood pressure measurement is:

- $\geq 90$ th percentile systolic and/or diastolic for gender-specific age and height charts from the National Heart and Lung Institute (NHLI) for subjects under 13 years or
- $\geq 120$  mmHg systolic or  $\geq 80$  mmHg diastolic for subjects 13 through 17 years,

at least 5 minutes rest should be allowed after the first measurement; then two additional blood pressure measurements are to be performed consecutively. The average of the three blood pressure measurements, systolic and diastolic, is the final blood pressure measurement and this average is the one to be entered into the EDC. All of the three blood pressure measurements with documentation of the time starting the resting and the time at which the two additional blood pressures are measured should be source documented.

If the subject is reporting symptoms of orthostatic hypotension when standing up after the blood pressure measurement, then the subject will be asked to lie down for 5 minutes, blood pressure and pulse rate will be measured, then the subject will be asked to stand and blood pressure and pulse rate measurements will be repeated after standing 1 to 3 minutes in order to measure the severity of the orthostatic hypotension. Vital signs will be collected at Baseline, at all visits from Week 2 through Week 52, and at unscheduled visits.

#### **6.4.3 Electrocardiograms**

All 12-lead ECGs will be complete, standardized recordings, performed in triplicate whenever possible at Baseline, and at all visits from Week 2 through Week 52 visits. The involvement of experienced personnel in the conduction of ECG recording in this population is strongly recommended.

Electrocardiograms should be performed before blood sampling or at least 30 minutes after blood sampling. The subject must rest in a sitting or supine position for 5 minutes before the ECG is obtained. Mild sedation is allowed exceptionally for ECGs (e.g., alprazolam at a pediatric-appropriate dose per age, and the *lowest dose* deemed necessary by the Investigator)

just in cases when the subject's agitation/anxiety does not allow a safe and accurate measurement and the Investigator, with agreement from the caregiver, considers it safe and appropriate for the subject. ECG tracings (paper or electronic) will be reviewed and interpreted by a qualified clinician. ECG tracings and results (ventricular rate, PR, QRS, QT, QTcF, and corrected QT interval using Bazett's correction method [QTcB] intervals) will be included in the subject's study records.

Eligibility at Baseline should be based on ECG tracings collected on the study-provided ECG device during the visit and on the ECG central read. All ECGs will be centrally read; the cardiology central overread is considered final. The QTcF/QRS as well as other exclusionary values and abnormalities of all the tracings of adequate quality will be reviewed to determine eligibility.

A maximum of one repeat ECG procedure is allowed at Baseline.

#### 6.4.4 Laboratory Evaluations

Clinical laboratory sample collection (including HbA1c) is encouraged, but not required, to be completed under fasting conditions. The laboratory evaluations will include, but are not limited to, the following:

- Clinical chemistry serum tests
  - Sodium (Na), potassium (K), carbon dioxide (CO2), chloride (Cl), phosphorus (P), calcium (Ca), blood urea nitrogen (BUN), creatinine (CR), glucose, albumin (ALB), total protein
    - *In Italy only:* [REDACTED]  
[REDACTED]  
[REDACTED]  
[REDACTED]  
[REDACTED]  
[REDACTED]  
[REDACTED]  
[REDACTED]
  - Alanine aminotransferase (ALT), aspartate aminotransferase (AST), gamma-glutamyl transpeptidase (GGT), alkaline phosphatase (ALP), total bilirubin (TBIL), lactate dehydrogenase (LDH)
  - Lipid panel

- Total cholesterol, high-density lipoprotein (HDL)-cholesterol, triglycerides, low-density lipoprotein (LDL)-cholesterol, cholesterol/HDL ratio, non-HDL cholesterol
- HbA1c
- Prolactin
  - Prolactin CCI  
[REDACTED] Results will be monitored CCI  
[REDACTED]
- Creatine kinase (CK)/creatine phosphokinase (CPK)
- Pregnancy test
  - A urine pregnancy test should be performed at all designated visits ([Table 6–1](#)) for women of child-bearing potential. If positive, the result will be confirmed with a serum pregnancy test.
    - If urine cannot be obtained in women of childbearing potential, a serum pregnancy test should be done in its place
- Hematology tests
  - Complete blood count (CBC) including:
    - White blood cell (WBC) count
    - Complete differential (relative and absolute)
    - Hematocrit (Hct), hemoglobin, red blood cells (RBC), platelets
    - Reticulocyte count
- Urinalysis
  - Blood, RBCs, WBCs, protein, glucose, ketones, specific gravity, pH
  - Reasonable efforts should be made to collect a urine sample from all subjects. When collection of a urine sample proves impractical or impossible (e.g., because the subject is incontinent or unable to cooperate), failure to collect a urine sample should be recorded in the subject's eCRF, and will not be considered a protocol deviation.
- Urine toxicology screen
  - Urine toxicology screen will test for controlled substances. The following controlled substances may be tested with a urine toxicology screen according to the schedule presented in [Table 6–1](#): amphetamine, barbiturates, benzodiazepines, cocaine, methadone, morphine/opiates, methamphetamine, marijuana (tetrahydrocannabinol [THC]), phencyclidine (PCP), ecstasy (3,4-methylenedioxymethamphetamine [MDMA]). A negative drug screen is required for study eligibility.

- Subjects who test positive and have a valid prescription for a controlled substance may be retested if they agree to abstain from the medication for the length of their participation in the study. The repeat test, and any other tests, must be negative for them to participate in the study.

Laboratory evaluations will be completed according to the schedule presented in [Table 6–1](#) and procedures detailed in the study laboratory manual. Additional safety testing may be performed at the discretion of the Investigator or designee.

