## **4 SUBJECT ELIGIBILITY AND WITHDRAWAL CRITERIA**

To be eligible for this study, subjects must meet all of the inclusion criteria and none of the exclusion criteria to enter this open-label extension study.

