## **4.2 Exclusion Criteria**

A subject must meet none of the following exclusion criteria to be eligible for the study:

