### ***CNS, Psychiatric, and Illicit Drug Use Criteria***

2. Requires treatment with a medication prohibited by the protocol, including concomitant psychotropic drugs targeting irritability, including those used off-label (clonidine, guanfacine, and propranolol; lithium, valproate), medications that prolong the QT interval; and strong cytochrome P450 (CYP) 3A4 enzyme (CYP3A4) inhibitors and inducers (see [Appendix A](#) and [Appendix B](#))
3. Is at a significant risk of suicide, or is a danger to self or others, in the opinion of the Investigator based upon all available sources of information including C-SSRS (positive answer to suicidal ideation questions 4 or 5 [or positive answer to suicidal behavior questions at Baseline])
4. Is at risk of significant violent behavior to the extent that participation would pose an undue risk to other patients, caregivers, or others in the opinion of the Investigator
5. Has a positive urine drug test at Baseline. For study eligibility, the urine toxicology (drug) screen (UDS) must be negative for any substance for which the subject does not have a valid prescription.

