Anxiolytics	PROHIBITED 
 
chlordiazepoxide
 
diazepam
 
flurazepam
 
 RESTRICTED 
 
alprazolam
 
lorazepam
 
midazolam
 
	Prohibited throughout the treatment period 
 
Mild sedation is allowed exceptionally for ECGs and blood draws during the study (e.g., alprazolam at a pediatric-appropriate dose per age, and the lowest dose deemed necessary by the Investigator) just in
 

Medication Class	Medication a	Prohibition/restrictions
	
 
• oxazepam
 
• temazepam
 
• triazolam
 
	
cases when the subject's agitation/anxiety does not allow a safe and accurate measurement and the Investigator, with agreement from the caregiver, considers it safe and appropriate for the subject.
 
 
• Short- or medium-acting benzodiazepine may be used for acute anxiety
 
• May not be used within 12 hours prior to an assessment visit
 
• Lorazepam, in doses according to age, may be used as a rescue medication for a maximum of 7 consecutive days. Reassessment and discussion with Medical Monitor is required if needed beyond 7 days. 
 
○ If lorazepam is not available, another benzodiazepine from the restricted list may be used
 
 
 

Beta blockers	PROHIBITED 
 
• propranolol
 
	Prohibited throughout the treatment period
Centrally-acting alpha-agonist hypotensive agents	PROHIBITED 
 
• clonidine
 
	Prohibited throughout the treatment period
Centrally-acting alpha2A adrenergic receptor agonists	PROHIBITED 
 
• guanfacine
 
	Prohibited throughout the treatment period

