Hypnotics and sleeping agents	PROHIBITED 
 
• eszopiclone
 
• zolpidem
 
• zopiclone
 
 RESTRICTED 
 
• melatonin
 
• ramelteon
 
• zaleplon
 
	
Prohibited throughout the treatment period
 
May not be used within 12 hours of a cognitive assessment, and efforts should be made to limit agents to lowest dose for the shortest time needed. 
 
○ Melatonin is allowed (≤5 mg/day) for insomnia
 
 

Non-stimulant ADHD medications	RESTRICTED 
 
• atomoxetine
 
	Allowed if stable throughout the antecedent study and the dose is expected to remain the same throughout the duration of the study.
Opioids	PROHIBITED 
 
• methadone
 
	Prohibited throughout the treatment period
Serotonin antagonists	PROHIBITED 
 
• cyproheptadine
 
	Prohibited throughout the treatment period

Medication Class	Medication a	Prohibition/restrictions
Stimulants and wake-promoting agents	RESTRICTED 

• amphetamine salts

• armodafinil

• lisdexamfetamine

• methylphenidate

• modafinil

	Allowed if stable throughout the antecedent study and the dose is expected to remain the same throughout the duration of the study.

Abbreviations: ADHD=attention-deficit hyperactivity disorder; ECG=electrocardiogram; QTcF=corrected QT interval using Fridericia's correction method; QRS=QRS interval on ECG; QT interval=QT interval on ECG

a Medications within each class include but are not limited to the examples listed in this table.

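### Protocol Section 6.4.4 sets a stricter drug-screen rule than exclusion criterion 5, and would exclude, or take off treatment, a subject on a stable prescribed amphetamine salt that Appendix A allows

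*Protocol*

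**What the plan says.** Two places in the protocol say what a Baseline urine drug screen must show.

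- **Section 4.2, exclusion criterion 5** (same wording in the synopsis). It opens by excluding a positive Baseline test. It then defines the eligibility test: the screen "must be negative for any substance for which the subject does not have a valid prescription".
- **Section 6.4.4, Laboratory Evaluations.** "A negative drug screen is required for study eligibility". On prescriptions it adds: "Subjects who test positive and have a valid prescription for a controlled substance may be retested if they agree to abstain from the medication", for as long as they take part. It closes: "The repeat test, and any other tests, must be negative for them to participate in the study".

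The panel in Section 6.4.4 names ten substances or classes that may be tested, amphetamine and benzodiazepines among them.

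Appendix A classes amphetamine salts as restricted, meaning usable under conditions. The condition is "Allowed if stable throughout the antecedent study and the dose is expected to remain the same throughout the duration of the study". For the restricted anxiolytics it says, among other conditions, "Short- or medium-acting benzodiazepine may be used for acute anxiety". Section 4.8.2.1 asks that permitted concomitant medications stay at a stable dose during treatment.

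On the standing of the criteria, Section 4 says "subjects must meet all of the inclusion criteria and none of the exclusion criteria to enter this open-label extension study", and Section 4.2 introduces its list with "A subject must meet none of the following exclusion criteria to be eligible for the study".

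**The concern.** Both texts speak to eligibility, and both deal with a positive result explained by a prescription. They decide it differently. Exclusion criterion 5 lets it pass. Section 6.4.4 does not, unless the drug is stopped and a repeat test is negative.

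The harm could run either way. A site that follows Section 6.4.4 may turn away a child who finished the antecedent study and meets the listed criteria, or may have a stable stimulant stopped so that the child can enter. A site that follows exclusion criterion 5 may later be told that the subject was ineligible. Section 10.6 treats that as a major deviation, with discontinuation unless stopping poses an unacceptable medical risk. The same section rules out eligibility waivers.

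**Working it through.** There is no plan figure to reproduce and no formula applies. The check sets the texts side by side for one subject.

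**Test case.** A subject has taken a prescribed amphetamine salt at an unchanged dose through the antecedent study and expects to stay on it. Amphetamine is included in the Baseline test.

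1. *Is the subject still on the drug when screened?* Yes. Section 3.1 makes the antecedent end-of-treatment visit the Baseline visit of this study, and Table 6–1 places the screen and dipstick there. A subject who meets the Appendix A condition is still taking the drug at that visit. The working case is that the test is then positive.
2. *Apply each rule.*

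| Text | Result for this subject |
|---|---|
| Exclusion criterion 5 (Section 4.2, synopsis) | Not excluded: the substance is prescribed |
| Appendix A, stimulants | Drug allowed, dose to stay the same |
| Section 4.8.2.1 | Permitted drugs to stay at a stable dose |
| Section 6.4.4 | Excluded, unless the drug is stopped for the whole study and the repeat test is negative |

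3. *Can the subject satisfy Section 6.4.4 and keep the drug?* No. The only route it offers to a positive subject is abstinence plus a negative repeat test. That removes the Appendix A allowance for this subject and runs against the stable-dose aim of Section 4.8.2.1.
4. *Does another text settle it?* No. Section 6.1 provides for site and sponsor review of eligibility but does not say which rule the reviewers apply. SAP Section 14.2 repeats the abstain-and-retest sentence, omits the sentences that require a negative result, and ranks nothing.

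**How wide is the case?** Appendix A names five stimulant or wake-promoting drugs: amphetamine salts, armodafinil, lisdexamfetamine, methylphenidate and modafinil. Only amphetamine salts match a panel item by name. Benzodiazepines are a secondary case. Six are restricted rather than prohibited (alprazolam, lorazepam, midazolam, oxazepam, temazepam, triazolam), but for short-term uses such as acute anxiety, procedural sedation or rescue, and with a 12-hour limit before assessment visits. They are not described as stable maintenance drugs.

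**Does any analysis depend on it?** The Safety Analysis Set is everyone dosed with open-label drug. The sample size is not based on power. SAP Section 14.2.1.3 puts drug-screen results in a listing only. The rule affects who may enrol, not how the data are analysed.

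**The case against.** The strongest reply is that the documents already point to one answer. Section 4 is where eligibility is defined, exclusion criterion 5 appears there and in the synopsis in the same words, and Section 6.4.4 is a laboratory subsection. Joint review by site and sponsor also makes it less likely that sites diverge. This has weight and favours exclusion criterion 5. It does not close the point, because Section 6.4.4 states its rule as an eligibility requirement and addresses prescription holders directly.

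A second reply is that the opening sentence of exclusion criterion 5, read alone, agrees with Section 6.4.4. The sentence that follows it narrows the test to unprescribed substances, so this reply fails.

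A third is that the panel lists what may be tested. That stands as a limit: the conflict arises only when amphetamine is actually tested.

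Some stronger readings are tempting but not supported:

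- *That no subject can satisfy both rules.* A prescription holder who abstains and retests negative meets both. One rule is stricter than the other; they are not logically incompatible.
- *That there is no time to retest.* Eligibility must be settled before enrolment (Table S-1, note e) and the first dose is planned for the day after Baseline (Section 3.1.1). But Section 6.4.4 provides for a retest and no deadline is given.
- *That barbiturates raise the same conflict.* Phenobarbital is among the moderate inducers that Appendix B allows with caution, but the prohibited anticonvulsants in Appendix A are examples only. Its status is unclear, so no contradiction is shown.

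**Conclusion.** The point holds. Section 6.4.4 is stricter than exclusion criterion 5, and for a subject on a stable prescribed amphetamine salt it defeats an allowance that the protocol makes in Appendix A. No text says which rule governs.

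The size is unknown. The documents give neither the number of subjects taking amphetamine salts nor the drug-screen rule of the antecedent study. The Appendix A condition, tied to stability through that study, shows that such subjects were foreseen, not how many there are. A reader might infer a material loss of enrolment or precision; the documents do not support that, and no planned analysis changes. Confounding from a stopped stimulant is a lesser matter, since exclusion criterion 7 lets the investigator exclude for a change in treatment status and Section 4.8 has medications recorded from Baseline.

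The conclusion assumes that amphetamine is tested and that the prescribed drug produces a positive result. The documents do not state which rule the sponsor intended. The repeated wording of exclusion criterion 5 and the Appendix A allowance make the looser rule the better reading.

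**What to change.** In Protocol Section 6.4.4:

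- Replace the sentence requiring a negative screen with a cross-reference to exclusion criterion 5, so that the screen need be negative only for substances without a valid prescription.
- State that prescribed drugs remain subject to Section 4.8.2.1 and Appendices A and B. The new text should not loosen the stable-dose rule in Section 4.8.2.1, or it would create a fresh conflict.
- Limit the abstain-and-retest text to drugs that those appendices prohibit, or delete it.

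Align the matching sentence in SAP Section 14.2. If the sponsor did intend the stricter rule, the change belongs instead in exclusion criterion 5 and Appendix A, so that all three agree.

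The cost is a text amendment with the ethics submission that Section 10.7 requires, in a study planned for about 60 sites in about eight countries. No assessment or analysis is added.
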